Target carbohydrate antigens expressed on breast cancer cells: Tumors expressing high levels of certain types of TACAs exhibit greater metastasis than those expressing low levels of these antigens, and this negatively impacts prognosis (27-29). In breast cancer, the LeY, STn, and KH-1 antigens, as well as selected gangliosides, glycosphingolipids and Globo-H carbohydrate antigens, are considered prime vaccine candidates because of their tissue distribution (30, 31). In particular, LeY has long been recognized as a potential target for immunotherapy because it is expressed in 70–90% of tumors of epithelial origin (32). The abundant gangliosides include GM3, GM2, GM1, and GD2, GD3 and GT3 (33). Antibodies to TACAs mediate a variety of effector functions and might lend to cross-presentation of tumor antigens to stimulate anti-tumor cellular responses. At present, LeY-conjugate vaccines appear to have only a limited ability to induce anti-LeY immune responses in humans (1). Our *in vitro* studies demonstrate that peptide mimotopes of LeY and gangliosides induce serum antibodies in mice that recognize the appropriate carbohydrate antigens on human or murine breast cancer cell lines (25, 34). Our *in vivo* studies demonstrate that the peptide mimotopes induce sustained immunity to these antigens (8, 25, 26). Collectively, these data provide the experimental foundation for evaluating peptide mimotopes as potential cancer vaccines in subjects with breast cancer.

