⁵The DTH skin test at prestudy will test the subjects' immunocompetency. Control antigens, Trichophyton Antigen and Candida antigen, will be administered id and the resulting induration will be ready at 48 - 72 hours post injection.

⁶ The DTH skin tests on weeks 5, 9 and 21 will test the DTH response to Mimotope P10s-PADRE. Trichophyton Antigen and Candida antigen will be administered id alongside Mimotope P10s-PADRE as control antigens to assess immunocompetency. DTH skin test indurations will be read at 48 – 72 hours post injection.

⁷ Visits must occur at set time points mentioned in the study calendar (+/- 3 days) with the exception of reading the skin test which must occur 48-72 hours post administration.

⁸ Concomitant medications will be collected from registration to end of treatment.

⁹ Post vaccine administration, the following vital signs will be monitored every 15 minutes (+/- 5 minutes) for one hour: blood pressure, temperature, and pulse.

¹⁰ Follow up visits shall begin with the next scheduled standard of care appointment and then shall occur every six months for five years and then yearly until death.

11. Criteria for Evaluation

Primary Objective – Safety:

- **Determination of DLT:** See Section 8, “Risks and Toxicities to be Monitored”. Any event that meets the dose limiting criteria will be determined a dose limiting toxicity.

Secondary Objectives – Immune Response:

- **Immunological Evaluation:** Serum will be collected at the Study Lab time points indicated in the study calendar in Section 10. Samples will be collected and stored by the UAMS Cancer Institute Tissue Bank following established Tissue Bank SOPs. IgM and IgG titers to TACAs will be evaluated by ELISA on TACA adhered to plates and FACS analysis of TACA adhered to liposomes. A positive TACA-directed immune response will be defined as an anti-TACA serum antibody titer of 1:40 for a baseline pre-vaccination titer of 0 or a \geq 4-fold increase over baseline titer > 0 (1, 11). Subjects will be judged to have had an adequate immune response if they have a positive TACA-directed immune response at any one of the first five designated time points following vaccine administration (Weeks 2, 3, 4, 7 and 9). The value of a booster immunization will be determined by anti-TACA IgM and IgG titers obtained from study labs collected on week 21.

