FACS analysis. Titer will be defined as the highest serum dilution yielding an $OD_{405} \geq 0.15$, in accordance with previous studies (1) or an MFI two standard deviations higher than background. A positive TACA-directed immune response will be defined as an anti-TACA serum antibody titer of 1:40 post-vaccination when the baseline pre-vaccination titer was 0, or a ≥ 4 -fold increase in titer post-vaccination when the baseline titer was greater than 0. The number and proportion of positive TACA-directed immune responses at each time point will be reported, both overall and by dose cohort. The number and proportion of subjects with at least one positive TACA-directed immune response will also be reported, both overall and by dose cohort. Medians and quartiles of titer will also be reported at each time point for any dose cohort of size 6.

To meet the secondary objective of analyzing the DTH response, we will measure the induration in mm across two diameters at the injection sites of the mimotope and control antigens. This will be done for each study subject at all indicated time points on the study calendar. An induration of >5 mm across at least one diameter will be considered a positive DTH response to that antigen at that time point. The number of subjects who show at least one positive DTH response to mimotope during the study will be reported as the number and proportion in each dose cohort. The number of positive DTH responses to mimotope at each time point will be reported as the number and proportion in each dose cohort. Positive DTH responses to the control antigens will be summarized the same way. Additionally, the two induration measurements per injection site, as well as their product (in mm^2), will be graphed as subject profiles over time, and summarized by antigen, dose group, and time as means and standard deviations.

To meet the secondary objective of determining sustainability of the immune response, the subject's TACA-directed immune titer at Week 19 will be compared to her TACA-directed immune titer at Week 9. The number and percentage of subjects with a sustained immune response will be reported in the aggregate and by dose cohort if more than one dose cohort is enrolled. In addition, the ratio of week-19 and week-9 titers will be plotted as dot plots and summarized as the mean, median and range.

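### One unconfirmed positive titre at any of five visits makes a subject a responder, and the plan does not say which antigen, isotype or assay decides

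*Combined protocol and SAP*

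**What the plan says.** Section 11 (Immunological Evaluation) classes a subject as an adequate responder if she is positive "at any one of the first five designated time points following vaccine administration", namely Weeks 2, 3, 4, 7 and 9. Section 12.a repeats the rule. Neither section asks for a second positive.

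On measurement, Section 11 says: "IgM and IgG titers to TACAs will be evaluated by ELISA on TACA adhered to plates and FACS analysis of TACA adhered to liposomes". That makes four titre series per antigen (two isotypes, two assays). Section 12.b defines titre by an OD cut-off, "in accordance with previous studies (1) or an MFI two standard deviations higher than background". The two assay criteria are joined by the word 'or', with no rule for discordant results.

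On positivity, Section 12.b says: "A positive TACA-directed immune response will be defined as an anti-TACA serum antibody titer of 1:40 post-vaccination when the baseline pre-vaccination titer was 0", or at least a 4-"fold increase in titer post-vaccination when the baseline titer was greater than 0". There is one pre-study baseline and no control arm.

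No section lists the antigens that make up the endpoint. Section 3 only names candidates: "In breast cancer, the LeY, STn, and KH-1 antigens, as well as selected gangliosides", among others.

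On reporting, Section 12.b says: "The number and proportion of subjects with at least one positive TACA-directed immune response will also be reported, both overall and by dose cohort". It also reports positives at each time point, and medians and quartiles of titre for any cohort of six. None of these summaries is stated to be split by antigen, isotype or assay.

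**The concern.** Secondary objective 1 asks whether the vaccine generates a humoral response against tumour-associated carbohydrate antigens. The proportion of subjects with at least one positive is a main summary bearing on that question. A rule that takes the best of several noisy measurements, all compared with the same single baseline, will label some subjects with no true change as responders. With no control arm, a false responder cannot be told from a true one within the trial.

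Two features drive the size of the error. The first is stated: any one of five visits suffices, unconfirmed. The second is a gap: the plan leaves open whether one series decides or whether a positive in any isotype, assay or antigen will do. If that choice is made after the titres are seen, the proportion becomes harder still to interpret.

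**Working it through.** **Plan's own figure.** The documents state no false-positive rate, null response rate or assay error for this endpoint, so there is nothing to reproduce.

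**Inputs from the documents.** Five post-vaccination visits; four series per antigen (2 isotypes x 2 assays); one baseline; positive at a rise of at least 4-fold when baseline is above 0.

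**Assumptions, none given in the documents.** Two-fold dilution steps, so that 4-fold is two steps; no true change in titre; true log2 titre spread evenly within a dilution step; normal error on the log2 scale with SD 0.3, 0.4, 0.5 or 0.7. The branch for a baseline titre of 0 (positive at 1:40) is not modelled.

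**Comparisons.** One series gives 5 comparisons. If any series for one antigen may count, there are 5 x 4 = 20.

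**Why simulate.** For independent comparisons with false-positive rate p, the chance of at least one is 1 - (1 - p)^k. At SD 0.5, p is about 2.5%, so:
- k = 5: 1 - 0.975^5 = 11.9%
- k = 20: 1 - 0.975^20 = 39.7%

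The visits share one baseline and the series share one serum sample, so independence overstates the result. Simulation with a shared baseline gives 8.7% and 29.9% at the same SD.

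**Chance that a subject with no true change is labelled a responder (simulated).** The four-series range runs from correlation 0.8 between series (lower figure) to 0 (upper figure).

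| Error SD (log2) | One series, any of 5 visits | Any of four series, one antigen |
|---|---|---|
| 0.3 | 0.5% | about 2% |
| 0.4 | 3% | 9-13% |
| 0.5 | 9% | 20-30% |
| 0.7 | 22% | 42-63% |

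With three antigens (an assumed number) and any series counting, the ranges at SD 0.4, 0.5 and 0.7 are 17-33%, 33-66% and 57-95%; at SD 0.3 the figure is about 6% under independence.

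**In subjects.** In a cohort of six with no true change, SD 0.5 gives 6 x 0.09 = 0.5 expected false responders if one series decides, and 6 x 0.20 to 6 x 0.30, or 1.2 to 1.8, if any of four may count.

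**Effect of requiring two consecutive positives in the same series.** At SD 0.4, 0.5 and 0.7:
- one series: 3.3%, 8.7% and 21.9% fall to 0.4%, 1.6% and 5.6%
- any of four independent series: 12.6%, 29.9% and 62.9% fall to 1.7%, 5.8% and 20.5%

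A route that also accepts an isolated positive if it repeats on fresh assay of both the baseline and the later sample adds roughly 5 x p x p per series. With p = 0.87%, 2.5% and 7.3%, that is about 0.04%, 0.3% and 2.7%. This assumes that the error arises in the assay and is independent on repeat.

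**The case against.** A reader might infer that the plan sets a 20-way rule per antigen, so that noise will label many non-responders as responders. The documents do not support that. Sections 11 and 12.a pool explicitly only over the five visits. That a positive in any isotype, assay or antigen suffices is a permitted reading, not a stated rule. On the stated pooling with one series, the chance is 0.5% to 22% over the assumed SDs.

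Nor is 'many' established. Every error size is assumed, and with a precise assay (SD 0.3) even the broadest one-antigen reading gives about 2%. Section 4.b commits to validating both assays before study samples are examined. The largest figures also need independence between series drawn from one serum sample, which is unlikely to hold fully.

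The consequences are limited too. Section 12.a calls the immunogenicity assessment qualitative because of sample size, no hypothesis test is planned, and Tables 1-3 in Section 7 act on dose-limiting toxicities alone. An isolated positive could show up in the per-visit counts.

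These objections remove the stronger claim but not the point. Validation is planned without a stated precision or false-positive limit. Per-visit counts separate visits but not isotype, assay or antigen, and do not confirm a positive. Titre medians and quartiles are promised only for cohorts of six. A qualitative purpose excuses low precision, but not a label whose false-positive rate is unknown.

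Separately, the Protocol Summary (Section 2) says that immune response in the first cohort at Week 9 also informs the dose decision, which Table 1 does not show. Those passages must be reconciled.

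**Conclusion.** The point holds as a limitation of a secondary, descriptive endpoint. The responder label rests on one unconfirmed positive at any of five visits against a single baseline, and the deciding antigen, isotype and assay and their combination are unspecified. Depending on assay precision, the false-responder chance runs from about 0.5% to 22% if one series decides. On the broadest one-antigen reading it runs from about 2% to 63%, and it is higher with more antigens. These figures rest on the assumed error SDs, two-fold dilutions and a baseline above 0.

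The documents do not show that the true rate is high, and the trial's primary safety objective is untouched. What follows is that the planned responder proportion alone cannot separate a vaccine effect from assay variation.

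**What to change.** In Sections 11 and 12.b:

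1. Fix the antigen list before samples are assayed, and report responder proportions separately by antigen, isotype and assay.
2. Add a confirmed-responder definition. A subject is confirmed in a given antigen-isotype-assay series if she is positive at two consecutive scheduled visits, or if an isolated positive at any visit repeats when the stored post-vaccination sample and the stored baseline sample are re-assayed together.
3. Keep the any-visit proportion as a second summary, so that brief responses stay visible.
4. Report assay precision from the planned validation, so that readers can place the trial within the range above.

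The cost is wording and a few repeat assays where serum remains; Section 9 provides for frozen storage for up to five years. No visits, subjects or doses change. The responder rate will be somewhat lower.

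Two limits remain. The two-visit route still leans on one baseline measurement. Pooling confirmed responders over many series would also raise the error again: with three antigens and independent series, two consecutive positives alone give about 5%, 17% and 50% at SD 0.4, 0.5 and 0.7. Reporting by series is therefore part of the remedy and not an optional extra.

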If the initial-cohort dose of 300 µg P10s-PADRE is declared to be the MTD and only 3 subjects were enrolled into the initial cohort, then this cohort will be expanded to 6 to assure that 6 subjects are treated at the MTD. The CRA for the trial will assign the subjects to cohorts and communicate the assignments to the research nurse, who will communicate them to the investigator. Only one cohort will be open to enrollment at a time. After the last non-boost dose in each cohort, the study will have a 3-week hold pending the cohort's DLT evaluation. Staggered dosing for the first two patients within each cohort will allow an interval of one week observation for toxicity following the first injection in the previous patient. The research pharmacist will be notified by orders of the registration and cohort dose. Expansion of the cohort to 6, or enrollment to the next cohort, may start once the previous 3 subjects complete their week-9 serology and are evaluated for DLT. Subjects who withdraw from the dose-escalation study without a DLT will be replaced. Subjects who withdraw from the dose- de-escalation study without a DLT will be replaced. Subjects who withdraw with a DLT will be considered evaluable for MTD determination.

8. Risks and Toxicities To Be Monitored

a. Potential Toxicities, Risks and Precautions:

Procedure	Risks	Measures to Minimize Risks
Complete history and physical exam, including blood chemistries	Identification of previously unknown condition	Qualified health care provider to evaluate potential subject Research records are kept in a locked area accessible only by study personnel.

Procedure	Risks	Measures to Minimize Risks

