Administration of study vaccine	
Experimental agent may be toxic or harmful.
 
First time use in humans
 
Risk of local reactions (i.e. swelling, redness, tenderness, itching, extravasations)
 
Potential for side effects ranging from hematologic toxicities and hypersensitivity reactions to anaphylaxis
 
Unanticipated risks
 
Unknown risks
	
Careful monitoring by clinic visits and 24 hour, 7 days per week physicians on call for unexpected problems
 
Only non-pregnant, non-lactating females may participate. The use of contraception during the study and the use of contraception for 18 months post completion of the trial are required.
 
Frequent laboratory tests including complete blood count (CBC) with differential, liver function tests, etc.
 
Close and frequent monitoring of subjects by qualified staff
 
DTH assay to monitor for hypersensitivity reactions
 
Emergency equipment including crash carts, advanced cardiac life support (ACLS) certified staff and rescue medications such as Benadryl, epinephrine, high dose steroids, etc. will be on-site during administration.
 
The Medical Monitor will review all toxicities on a regular basis and will be available to aid subjects as needed.
 
The study drug may be discontinued.
 
This research is being conducted at an experienced clinical research center.
 
Reporting and monitoring mechanisms are in place for AEs, serious adverse events (SAEs) and unanticipated problems.

Administration of MONTANIDE™ ISA 51 VG	
Dermatology/Skin: local erythema, rash, pruritis
 
Gastrointestinal: diarrhea, anorexia, nausea, vomiting, abnormal taste
 
Hepatic: elevated
	
Careful monitoring by clinic visits and 24 hour, 7 days per week physicians on call for unexpected problems
 
Only non-pregnant, non-lactating females may participate. The use of contraception during the study and the use of contraception for 18 months post completion of the trial are required.

Procedure	Risks	Measures to Minimize Risks

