a. Sample Size, Study Duration and General Considerations: Because each subject will receive multiple vaccine injections at a constant dose over an extended period of time, the second and third subject of *the same* dose cohort will be enrolled, as available, before the first subject has finished all scheduled injections. However, if two or more subjects are enrolled on the same day, then their injection schedules will be staggered at least one week apart. The decision to escalate or de-escalate the dose, expand the cohort, or terminate the study will be based on assessment for DLTs, which will require 9 weeks per subject. Upon evaluation of all subjects in a cohort (3-6/dose), dose escalation will proceed according to the schedule shown in **Tables 1, 2, and 3**. Except for the fact that they allow for possible de-escalation from the initial dose of 300 μ g, **Tables 1, 2, and 3** constitute the toxicity-based “traditional” design of Storer (43). The time to assess a cohort of 3 for DLTs is anticipated to be 13 weeks based on an accrual rate of 2 eligible Stage IV subjects per month. If no DLTs occur in the initial and final cohorts, then this study will require nine subjects. Subjects who withdraw from the dose-escalation study without a DLT will be replaced. Subjects who withdraw from the dose-de-escalation study without a DLT will be replaced. Subjects who withdraw with a DLT will be considered evaluable for MTD determination. Given the recruitment and immunization/evaluation schedule, we expect this study to be completed in a minimum of 12 and a maximum of 24 months.

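### The one-week stagger in 12.a is tied to same-day enrolment rather than to first-injection date, so on a plain reading of 7.g subjects 2 and 3 of a dose cohort may start less than a week apart.

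*Combined protocol and SAP*

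**What the plan says.** Section 7.g (Dose Assignment): "Staggered dosing for the first two patients within each cohort will allow an interval of one week observation for toxicity following the first injection". The rest of that sentence makes clear that the injection meant is the previous patient's.

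Section 12.a (Sample Size, Study Duration and General Considerations): the second and third subjects of a dose cohort "will be enrolled, as available, before the first subject has finished all scheduled injections". The paragraph then adds a condition: "if two or more subjects are enrolled on the same day, then their injection schedules will be staggered at least one week apart".

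No other text sets a minimum interval between first injections within a cohort. The three-week hold in 7.g acts between cohorts or before expansion. The same section says that expansion to six, or opening the next cohort, "may start once the previous 3 subjects complete their week-9 serology and are evaluated for DLT". Neither provision separates subjects 2 and 3.

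Footnote 1 of the Study Calendar (Section 10) allows up to 14 days from prestudy work to the first injection. That interval is bounded but not fixed.

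**The concern.** The risk table in Section 8.a lists "First time use in humans" for this vaccine and names reactions up to anaphylaxis. The purpose of a stagger is to let one woman's first week be seen before the next woman is exposed. What matters for that is the date of first injection. Section 12.a uses the date of enrolment instead, and only when two dates coincide.

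The results are uneven. Two women enrolled on the same day must start a week apart, while two enrolled a day apart may start a day apart or together. Section 7.g does refer to injection dates, but its plain wording stops at the second patient.

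At stake is the chance that subject 3 is injected before a reaction later in subject 2's first week has appeared. The hour of vital signs and the on-site rescue equipment deal with immediate reactions, not with that.

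**Working it through.** **The plan's own timing figure.** Section 12.a gives 13 weeks to assess a cohort of three, "based on an accrual rate of 2 eligible Stage IV subjects per month". With a 9-week DLT window and two gaps of 2 weeks (a 4-week month), 9 + 2 × 2 = 13 weeks. With a calendar month it is 9 + 2 × 2.17 = 13.3 weeks. The figure reproduces. It implies average spacing of about two weeks, so close starts are permitted but not inevitable.

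**The rules applied to dates.** Take equal times from enrolment to injection and count first injections from subject 1's.

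- Enrolment on days 0, 10 and 11: 7.g is met (10 days between subjects 1 and 2) and 12.a is not triggered. Subjects 2 and 3 start 1 day apart. Had both enrolled on day 10, 12.a would have required 7 days.
- Enrolment on days 0, 3 and 7: 7.g moves subject 2 to day 7, when subject 3 is also due. They enrolled on different days, so 12.a is silent. The gap is 0 days.

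**How often.** The rate of 2 per month is from 12.a. The rest is assumed: Poisson accrual, equal enrolment-to-injection intervals, dosing in enrolment order, and the plain reading of 7.g.

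Mean gap m = 30.44 / 2 = 15.22 days, and q = exp(−7 / 15.22) = 0.631. In continuous time:

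- Subjects 1 and 2 enrol at least 7 days apart, and subject 3 enrols within 7 days of subject 2: q(1 − q) = 0.631 × 0.369 = 0.233.
- Subject 2 enrols within 7 days of subject 1 and is held to day 7, and subject 3 enrols before day 14: (1 − q) − (7/m)q² = 0.369 − 0.460 × 0.399 = 0.185.
- Sum: 0.418.
- Less subjects 2 and 3 enrolled on the same calendar day, whom 12.a separates: 1 − m(1 − exp(−1/m)) = 0.032. This leaves 0.386.

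Counting in whole days removes about two more points. A simulation of 2,000,000 initial threes per rate, with whole days and both rules applied, gives:

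| Accrual per month | Subjects 2 and 3 under 7 days apart | Same day | Mean delay of last first injection under a 7-day rule |
|---|---|---|---|
| 1 | 19.4% | 2.2% | 0.8 days |
| 2 | 36.7% | 7.6% | 1.6 days |
| 3 | 50.5% | 14.5% | 2.4 days |

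The maximum delay is 7 days in each case.

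**Sensitivity.** Let the enrolment-to-injection interval vary independently and uniformly over 3 to 14 days (an assumption), with women dosed in order of readiness. The second and third women are then under 7 days apart in 19.2%, 35.3% and 48.1% of threes at 1, 2 and 3 per month. The result does not depend on equal intervals.

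**The other reading of 7.g.** If each of the first two patients counts as a previous patient, subject 3 waits a week after subject 2 and the proportion is 0%.

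**The case against.** The best objection is that 7.g may already cover subject 3. Its phrase about the previous patient can be taken to require a week's wait after each of the first two patients, and nothing in the protocol rules that out. This stands. The 37% is conditional on the narrower reading. Even so, 12.a would then suggest that spacing is needed only for same-day enrolment, and staff working from 12.a alone could miss the requirement.

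A second objection is that, on the narrow reading, the sponsor has simply chosen a single-sentinel design and promised nothing more. That is a tenable design. But 12.a does separate subjects 2 and 3 when they enrol on the same day, which makes it hard to see indifference to their spacing as intended.

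A third is that no rule would hold subject 3 if subject 2 reacted. Tables 1-3 act once the cohort has been evaluated. The stopping rules in Section 17.b need a death not related to cancer, two related Grade 4 toxicities, or three attributed SAEs. This also stands: the benefit runs through the investigator's judgement, just as it does for the existing wait between subjects 1 and 2.

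Some stronger readings are not supported:

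- **That 7.g and 12.a contradict each other.** They do not; both can be followed together.
- **That 37% is a probability of harm.** Harm would also need a reaction in subject 2, after the observed hour and before day 7, that would have changed subject 3's dosing. The documents give no rate for that.
- **That subjects 4-6 show the same fault.** They start only after three subjects at that dose have completed week-9 serology and DLT evaluation, so leaving them unstaggered is not an error.

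**Conclusion.** The point holds as a minor one and is best seen as a cheap improvement. The same-day trigger in 12.a follows the wrong date, and on the plain reading of 7.g nothing else keeps subjects 2 and 3 a week apart. Under that reading, with dosing in enrolment order, equal enrolment-to-injection intervals and Poisson accrual at 2 per month, about 37% of initial threes would have those two first injections less than 7 days apart (19% to 51% at 1 to 3 per month). On the wider reading of 7.g it is none, and the remaining task is to make 12.a agree.

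The exposure is narrow. If subjects are dosed in enrolment order, subject 3 is still at least 7 days after subject 1. The protocol does not state that order, so this too is an assumption. At 500 µg or 100 µg, the three subjects also follow a completed DLT evaluation at 300 µg. A reader might infer that the dose-finding conclusions are affected. They are not: the DLT definition, Tables 1-3 and the MTD determination do not depend on this interval.

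**What to change.** Put the same sentence in 12.a and 7.g: *Among the first three subjects of each dose cohort, including replacements, no subject will receive her first injection less than 7 days after the first injection of the previous subject.*

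This ties the interval to injection date, settles the reading of 7.g, and holds whatever the enrolment pattern or screening time. The existing same-day sentence in 12.a can stay.

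The cost is one sentence in two places and a small delay. At 2 per month the last first injection of an initial three moves later by a mean of about 1.6 days (maximum 7), or 1.6 / 7 = about 0.2 week on the planned 13. At 1 to 3 per month the mean delay is 0.8 to 2.4 days.
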